### 10.1.2 Non-efficacy monitoring

The DSMB will monitor the vaccine for non-efficacy defined as evidence that it is highly unlikely that the vaccine has a beneficial effect on acquisition of VE(0–24) or of VE(7–24) of 40% or more. Such analyses will start when two conditions are met: (1) all participants in follow-up have reached 13 months of follow-up since enrollment, and (2) at least 60 MITT infections have been observed. Condition (2) is chosen as the minimum MITT infection total at which a point estimate of zero VE would just correspond to an unadjusted upper 95% confidence bound for VE(0–24) equal to 0.40 based on a Cox proportional hazards model; the approach, stated in condition (2), to starting non-efficacy monitoring was suggested by [Freidlin, Korn, and Gray \(2010\)](#). Thereafter, non-efficacy interim analyses will proceed at every scheduled DSMB meeting (anticipated every six months) until the end of Stage 1.

The criterion for non-efficacy is that, for both VE(0–24) and VE(7–24), the lower 95% confidence bound lies below 0% and the upper 95% confidence bound lies below 40%. By checking confidence intervals for both VE(0–24) and VE(7–24), and requiring completed 13 months of follow-up, the monitoring plan is designed to protect against stopping prematurely based on ramping vaccine efficacy over the intercurrent period of 0–13 months.

At each non-efficacy interim analysis, VE(0–24) and VE(7–24) are estimated with 2-sided 95% unadjusted confidence intervals using the same method as for the final analysis of VE described in Section 8.1. Based on projected accrual and HIV-1 incidence in the placebo group, it is expected that some participants will have reached the Month 24 study visit by the time of the first non-efficacy interim analysis, such that VE(0–24) and VE(7–24), which are both defined based on cumulative incidence of HIV-1 infection through to the Month 24 visit, can be estimated. At the early interim analyses, however, it is possible that only very few participants will have reached the Month 24 study visit by the time of the analysis, precluding the ability to estimate VE(0–24) and VE(7–24) with adequate precision. In this event, cumulative vaccine efficacy through time  $\tau$ ,  $VE_{0-24}(\tau)$  and  $VE_{7-24}(\tau)$ , will be estimated with fixed time point  $\tau$  chosen to be the latest possible time point where stable estimation of both VE parameters can be achieved; this is operationalized by defining  $\tau$  as the maximum time point when at least 150 participants in the per-protocol cohort are observed to be at risk for the primary efficacy endpoint in each treatment arm.

In all interim analyses of VE, participants who have not experienced the primary endpoint will be right-censored at the time of their last visit.

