6.9.5 Vaccine efficacy analyses

6.9.5.1 Primary vaccine efficacy analysis: HIV-1 infection

The primary analysis will be done in the PP population where participants becoming HIV infected or dropping out before the visit after the third vaccination or not having received all of the first 3 vaccinations within the specified time window or having a major specified protocol deviation, will be excluded from the analysis. The date of HIV-1 diagnosis will be the draw date of the first sample that leads to a positive test result by the diagnostic algorithm described in Section 10.3. Dropouts will be censored at the time of their last HIV-1 negative test. To evaluate the primary vaccine efficacy endpoint, the ratio of cumulative incidences of HIV-1 infection between Months 7 and 24 (vaccine vs. placebo), estimated using the transformed Nelson-Aalen cumulative hazard function estimator and tested via a Wald test. Cox proportional hazards model will also be used for estimating VE(7-24), measured by 1 minus the hazard ratio (vaccine vs. placebo) and for score testing whether the VE(7-24) differs from 0%.

As a sensitivity analysis to the primary analysis of vaccine efficacy in the PP population, targeted minimum loss-based estimation (TMLE) is used to estimate of this vaccine efficacy parameter. In particular, TMLE is used to estimate the cumulative incidences of HIV-1 infection over time for each of the vaccine and placebo groups, through to the final timepoint Month 24. These estimates will then be contrasted to estimate the primary VE parameter VE(7-24), which adjusts for covariates. This analysis has the ability to correct for bias due to measured participant covariates that predict both per-protocol status and HIV-1 infection. Iterative mean-based TMLE is used for this analysis as described in Benkeser et al. (2016, PhD dissertation). As part of the implementation of the TMLE the Super Learner is used to generate initial estimates of the conditional censoring distribution and the iterated conditional means [48]. The Super Learner library includes both parametric and nonparametric learning algorithms that are specified in the

SAP; the SAP also specifies the input variables considered by the different learning algorithms. Each learning algorithm considers adjustment for baseline demographic covariates and the baseline behavioral risk score built via supervised learning.

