8.8 Final disposition of study products

All unused study products must be returned to the sponsor or destroyed after the study is completed or terminated according to the instructions provided in the Site Investigational Product Procedures Manual.

9 Clinical procedures

The schedule of clinical procedures is shown in Appendix G and Appendix H.

All study data will be recorded on paper source documents prior to being entered into the study database (see the HVTN 705/VAC89220HPX2008 SSP).

During the COVID-19 pandemic, procedures are in place so that study visits may be conducted remotely, such as via phone, text message, email, or other electronic means, in lieu of, or in combination with, in-person visits (see HVTN 705/VAC89220HPX2008 SSP for additional details).

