Appendix G Schedule 1: Procedures at HVTN CRS for HIV-uninfected participants

Visit:	011	02 ²	03	04	0511	06	07	08	09	10	11	12	13	14	15	16	17	Post
Day:		D0	D84	D168	D169	D196	D273	D364	D394	D455	D546	D637	D728	D819	D910	D1001	D1092	1031
•																		
Month:		M0	M3	M6	M6	M7	M09	M12	M13	M15	M18	M21	M24	M27	M30	M33	M36	
Procedure	Scr.	VAC1	VAC2	VAC3				VAC4										
Study procedures ³																		
Signed screening consent (if used)	X		_															
Assessment of understanding	X		_	_												_		
Signed protocol consent	X																	
Medical history	X																	
HIV risk assessment	X		_			_												
Complete physical exam	X		_	_		_									_	_	X	
Abbreviated physical exam	_	X	X	X	X	X	X	X	X	X	X	X	X	X	X	X		
Risk reduction counseling	X	X	X	X	_	X	X	X	X	X	X	X	X	X	X	X	X	
Pregnancy prevention assessment ⁴	X	X	X	X	_	X	X	X	X	X	_	_	_	_	_	_	_	
Behavioral risk assessment questionnaire	_	X	_	_	_	X		X	_	_	_	_	X	_	_	_	X	
Confirm eligibility, obtain demographics, randomize	X	_	_					_		_							_	
Social impact assessment	_	X	X	X	_	X	X	X	X	X	X	X	X	X	X	X	X	
Outside testing and belief questionnaire	_	_	_	X	_	_		_		_	_	_	X	_			_	
Concomitant medications	X	X	X	X	X	X	X	X	X	X	X	X	X	X	X	X	X	
Intercurrent illness/adverse experience	_	X	X	X	X	X	X	X	X	X	X	X	X	X	X	X	X	
HIV infection assessment ⁵	X	X	X	X	_	X	X	X	_	X	X	X	X	X	X	X	X	
Confirm HIV test results provided to participant	_	X	X	X	_	X	X	X	X	_	X	X	X	X	X	X	X	X
Local lab assessment																		
Screening HIV test	X	_	_	_	_	_	_	_	_	_	_	_	_	_	_	_	_	
Pregnancy ⁶	X	X	X	X	_	_	_	X	_	_	_	_	_	_	_	X	_	_
GC/CT ⁷	_	X	_	X	_	_	_	X	_	_	X	_	X	_	X	_	X	_
Syphilis ⁷	_	X	_	X	_	_	_	X	_	_	X	_	X	_	X	_	X	_
Trichomonas vaginalis ⁷	_	X	_	X	_	_	_	X	_	_	X	_	X	_	X	_	X	_
Cervicovaginal secretion collection ⁷	_	X	_	X	_	_	_	X	_	_	X	_	X	_	_	_	_	_
Vaginal swabs ⁷	_	X	_	X	_	_	_	X	_	_	X	_	X	_	_	_	_	_
Hemoglobin (Hb) ⁸	X	_	_	X	_	_	_	X	_	_	_	_	_	_	_	_	_	
Vaccination procedures																		
Vaccination ⁹	_	X	X	X	_	_	_	X	_	_	_	_	_	_	_	_	_	
Reactogenicity assessments ¹⁰	_	X	X	X		_	_	X	_	_	_	_	_	_	_		_	
Poststudy																		
Unblind participant			_				_		_						_			X
16		1: 1 0																

¹ Screening may occur over the course of several contacts/visits up to and including day 0 prior to vaccination

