### 8.1 Primary Analysis of Vaccine Efficacy

The time between enrollment and the date of HIV-1 infection diagnosis determined in Section 5 is evaluated for all subjects. Subjects becoming HIV-infected or dropping out before their month 7 visit or not having received all of the first 3 vaccinations within the specified time window or having a major protocol deviation will be excluded from the primary PP analysis. **The failure times of participants with last HIV-negative test at or after the month 24 visit are right-censored at the right edge of the month 24 allowable visit window [defined as 60 days after the target day (728 days) for the month 24 visit, equal to 25.91 months post-enrollment]. For participants with last HIV-negative test prior to the month 24 visit and without diagnosis of the HIV-1 infection primary endpoint at or before the month 24 visit, their failure times are right-censored at the date of the last HIV-negative test.**

We define the primary vaccine efficacy parameter,  $VE(7-24)$ , as one minus the probability of the primary efficacy endpoint between the month 7 and month 24 visit for the vaccine group divided by the probability of the primary efficacy endpoint between the month 7 and month 24 visit for the placebo group times 100 percent. **More specifically, the primary VE parameter,  $VE_{7-24}(\tau)$ , will be estimated at the fixed time point  $\tau = 25.91$  months post-enrollment with the specification of the value of  $\tau$  determined as noted above.** Each of the two cumulative incidence parameters in  $VE_{7-24}(\tau)$  will be estimated using the transformed Nelson-Aalen estimator for the cumulative hazard function evaluated at time  $\tau$  defined above. We will use the delta method to obtain the asymptotic 95% CI for the log cumulative incidence ratio (vaccine/control) and then back-transform these confidence bounds to the VE scale. Both the point estimate and the 95% CI for VE will be reported.

$VE(\tau)$  is the target parameter for the primary analysis of overall VE. The primary analysis tests

$$\begin{aligned} &\text{the null hypothesis } H_0: VE_{7-24}(\tau) = 0\% \text{ versus} \\ &\text{the alternative hypothesis } H_1: VE_{7-24}(\tau) \neq 0\% \end{aligned} \tag{1}$$

using a 2-sided  $\alpha = 0.05$  level Wald test of the equality of log cumulative hazard functions at  $\tau$  for the vaccine group and the control group.

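### SAP 10.1.2 censors interim follow-up at the last visit, against the last-HIV-negative-test rule used elsewhere; the effect is negligible unless testing was interrupted before a look

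*SAP*

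**What the plan says.** SAP 10.1.2 describes the interim estimates of VE(0-24) and VE(7-24) as made "using the same method as for the final analysis of VE described in Section 8.1". Where few women have reached Month 24, it replaces that month by tau, the latest time with at least 150 per-protocol women at risk in each arm. It closes with a rule for all interim VE analyses: "participants who have not experienced the primary endpoint will be right-censored at the time of their last visit".

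The other places that set a censoring date use the last negative test:

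- Protocol 6.9.5.1: "Dropouts will be censored at the time of their last HIV-1 negative test". SAP 5.3 repeats this.
- SAP 8.1, for women whose last negative test falls before the Month 24 visit and who have no endpoint: "their failure times are right-censored at the date of the last HIV-negative test". Women testing negative at or after Month 24 have a separate window-edge convention, which is not at issue here.

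Visits without an HIV test exist. In Protocol Appendix G the row "HIV infection assessment" is blank at visit 9 (Month 13), and Appendix E schedules no HIV diagnostics there. Protocol Section 9 adds that during the COVID-19 pandemic "study visits may be conducted remotely, such as via phone, text message, email, or other electronic means", in place of or combined with in-person visits.

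**The concern.** An infection can enter the data only through a test. If a woman's follow-up is extended from her last negative test to a later untested visit, she stays in the risk set over a period in which she could not be counted as a case. Cumulative incidence is then understated. Because tau depends on the number at risk, tau can also move to a month at which few women were tested.

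The timing makes this worth checking. SAP Section 9 gives May 25, 2021 as the last enrollee's target Month 24 visit (Day 728). Counting back 728 days gives enrollment on about May 28, 2019, and Day 394 (Month 13) falls on about June 25, 2020. That is close to the earliest date on which all women could have reached 13 months, one of the two conditions for the first non-efficacy look. Protocol version 4.0, which introduced remote visits, is dated June 12, 2020.

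What is at stake is what the DSMB is shown at interim looks: the placebo and vaccine incidence, the month through which VE is estimated, and VE itself. SAP 10.1.2 states that "the monitoring plan is designed to protect against stopping prematurely based on ramping vaccine efficacy over the intercurrent period of 0–13 months", so a rule that dilutes late follow-up deserves a check.

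**Working it through.** **The plan's own figure.** SAP 10.1.2 says 60 MITT infections is the minimum at which a VE estimate of 0% has an upper 95% bound of 40%. With 1:1 allocation, events = (1.96 × 2 / |ln 0.6|)² = 58.9, so 59. At 60 events the bound is 1 − exp(−1.96 × 2/√60) = 39.7%. The trigger reproduces and does not depend on the censoring rule.

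**Inputs (Protocol 6.4.1).** 2600 women, 1:1; accrual over 14 months, at half rate for the first 3; placebo incidence 4.2% per year (0.0035 per month); dropout 10% per year; VE 25% to Month 7 and 50% after; 5% outside the per-protocol set. First look at calendar Month 27 (14 + 13). The share of visits without an HIV test is not in the documents and is varied below.

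**In-person visits.** In 800 simulated trials per scenario with only the Month 13 gap, last-visit censoring adds 0.8% of person-time. VE changes by −0.16 to 0.00 points. The probability of meeting the boundary, last visit against last test, is 72.3% against 72.4% at VE 0% and 0.4% against 0.5% at VE 50%.

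**Scattered untested visits.** With up to 30% of visits untested at random, equally in both arms, person-time rises by 9.9%. VE moves by −0.65 to +0.45 points and the boundary probability by no more than about 1.5 points, in either direction. Both risk sets swell in the same proportion, so the ratio hardly moves.

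**Testing gap just before the look (assumed).** Results from 300 simulated trials under the design alternative, both rules on the same data:

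| Gap | Rule | tau (month) | Placebo incidence to tau | VE(0-tau) |
|---|---|---|---|---|
| none | both | 21 | 7.0% | 40.6% |
| 3 months | last test | 18 | 6.1% | 39.8% |
| 3 months | last visit | 21 | 5.6% | 38.7% |
| 6 months | last test | 15 | 5.1% | 38.2% |
| 6 months | last visit | 21 | 4.2% | 36.0% |

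The last-test rows can be checked by hand. True placebo incidence is 1 − exp(−0.0035 × t) = 7.1%, 6.1% and 5.1% at Months 21, 18 and 15. Last-visit censoring understates incidence to Month 21 by (7.04 − 5.55)/7.04 = 21% and (7.04 − 4.24)/7.04 = 40%.

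The part of the VE shift due to the censoring rule is 39.8 − 38.7 = 1.1 points and 38.2 − 36.0 = 2.2 points. A second run of 600 trials gave 41.2 − 39.9 = 1.3 and 38.4 − 36.2 = 2.2.

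**Why VE(0-tau) moves and VE(7-tau) does not.** Suppose a fraction f of the hazard after Month 7 is visible in both arms. On the hazard scale, to Month 21, the vaccine/placebo ratio is (0.75 × 7 + 0.5 × 14f)/(7 + 14f). With the 6-month gap, placebo incidence of 4.24% gives 7 + 14f = −ln(1 − 0.0424)/0.0035 = 12.38, so 14f = 5.38. The ratio is (5.25 + 2.69)/12.38 = 0.641, or VE 35.9%, in line with the simulated 36.0%. For Months 7 to 21 the ratio is 0.5 × 14f/14f = 0.5 for any f.

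**Stopping decision.** The boundary needs both VE(0-24) and VE(7-24) to meet the criterion. In 500 trials at the design alternative, last test against last visit:

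- 3-month gap: VE(7-tau) 46.7% against 46.5%; both criteria met in 0.6% against 0.6%.
- 6-month gap: VE(7-tau) 42.7% against 44.3%; both criteria met in 2.0% against 1.2%.

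The simulation error on 2.0% is √(0.02 × 0.98/500) = 0.6 points. Two other runs (500 and 600 trials) gave values between 0.2% and 1.4%, with differences between the rules within noise.

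**The case against.** The strongest reply is that this is a wording slip with no consequence. Much of that stands.

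- *The gap scenario is not documented.* Remote visits are permitted, not required; they may be combined with in-person visits; and Protocol 9.10 allows HIV testing at interim visits. A complete 3- or 6-month stop in testing is an assumption.
- *Other untested visits add little.* Visit 5 is one day after a tested visit. Blood drawn at Month 13 may be used for HIV diagnostics if necessary (Appendix E, footnote 13), and that visit is about one month after the Month 12 test. For early termination, Protocol 9.11 only asks staff to consider a test, but Appendix E footnote 8 says blood should be drawn for one.
- *The final analysis is not affected.* SAP 8.1 already censors at the last negative test where that precedes Month 24.

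A reader might infer that the rule pulls interim VE toward the non-efficacy boundary and risks stopping an effective vaccine. The documents do not support that. The boundary has two parts, VE(7-tau) shows no consistent shift, and the probability of meeting both parts does not rise. A consistent shift in both parameters would need unequal testing between arms. With 20% of visits untested in placebo and 10% in vaccine, VE moves by −2.4 to −4.8 points; with the reverse, by +2.1 to +4.2. Nothing in this blinded 1:1 trial suggests either.

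A reader might also set 38.7% and 36.0% against the 40.6% seen with full testing. That contrast mixes lost testing with the censoring rule. Last-test censoring would report 39.8% to Month 18 or 38.2% to Month 15, and cannot recover the missing months.

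What remains is the contradiction itself, and the overstated tau and understated incidence if testing was interrupted.

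**Conclusion.** The contradiction is certain: SAP 10.1.2 departs from Section 8.1, which it says it follows, and from SAP 5.3 and Protocol 6.9.5.1. Its severity is minor.

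The harm in the gap scenarios is to the description given to the DSMB: VE labelled as running to Month 21 when testing supports Month 18 or 15, and incidence low by a fifth to two fifths. The fall of 1 to 2 points in VE(0-tau) depends on the protocol's assumption of lower VE before Month 7; unchanged VE(7-tau) depends on constant VE after it.

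The simulations compare the two censoring rules on the same data. They are not a check of Protocol Table 6-4, whose simulation details are not fully stated. The rule covers all interim VE analyses, so it reaches the high-efficacy looks too; those were not simulated.

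**What to change.** Replace the closing sentence of SAP 10.1.2 with: *For every interim analysis of VE, a woman without the primary endpoint is right-censored at the date of her last HIV-negative test.* Add that, in choosing tau, a woman counts as at risk only up to that date.

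This SAP version is dated July 2022, after the target end of Stage 1 in mid-2021, so the practical step is to confirm which date the interim programs used. If it was the last visit, note this when the interim results are described.

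The cost is one sentence and one variable in the interim program. The downside is small: tau may be earlier when testing was interrupted.

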### 10.1.3 High efficacy monitoring

Monitoring of high efficacy allows early detection of a highly protective vaccine if there is evidence that  $VE(0-36) > 70\%$ . Stage 1 high efficacy analyses will be harmonized with those for non-efficacy monitoring, with the exception that the high efficacy analyses will only start once at least 150 participants in the MITT cohort have reached the terminal Month 36 visit.

This condition ensures that sufficient follow-up has accumulated to estimate VE(0–36). If Stage 2 occurs, there will also be one final high efficacy interim analysis at the midpoint of Stage 2, defined as 6 months after the end of Stage 1.

The criterion for high efficacy is that the unadjusted 95% confidence interval for VE(0–36) lies above 70%. Note that, while the potential harm and non-efficacy monitoring is restricted to infections diagnosed up to Month 24, the monitoring for high efficacy counts all infections up to Month 36 because early stopping for high efficacy would only be warranted under evidence for durability of vaccine efficacy.

## 10.2 Monitoring of the Use of PrEP

The use of oral FTC/TDF as PrEP (either off-study or provided in the study) may impact study outcomes (e.g., by lowering the HIV-1 incidence rate rendering a loss of statistical power). Dried blood spot (DBS) samples will be used for assessment of quantitative concentrations of intracellular tenofovir diphosphate (TFV-DP).

The prevalence of oral FTC/TDF use will be estimated and reported both as any detectable use and as effective use. More specifically, estimated percentages of person-years at-risk (PYR) during any detectable FTC/TDF use and during inferred effective FTC/TDF use will be reported.

Next we summarize how inferred effective use is measured. Current knowledge about PrEP in women indicates that consistent use of 6–7 doses a week is required to achieve protection. The lower quartile of simulated TFV-DP levels in DBS at 6 doses per week is 1064 fmol/punch (Castillo-Mancilla et al., 2013). In this trial, we will use 1,000 fmol/punch as the cut-off to define effective PrEP use based on the lower quartile cited above. Ongoing work with calibration of DBS from directly observed dosing studies may refine these thresholds. PrEP use measures will be reported by arm to the DSMB; in addition, both the OC and the protocol team leadership will see pooled estimates of FTC/TDF use.

DBS samples will be collected and stored for prospective monitoring of PrEP use at all study sites at pre-specified fixed sample collection days each month (see Section 10.2.1 for details). Furthermore, in order to increase the precision of PrEP use estimation, the frequency of sample collection may be increased.

At a given calendar time  $T$  (e.g., a fixed date prior to a scheduled DSMB meeting), we are interested in the population-level parameter, the percentage of person-years at-risk for HIV infection on effective PrEP use between initiation of DBS sample storage and time  $T$ . The definition of this parameter assumes that we have an assay readout from stored samples that accurately measures effective PrEP use as a binary outcome at the time the sample was drawn; importantly, it does not require an accurate measurement of effective PrEP use the day before or for any period of time earlier than the sampling day. In addition to estimating the percentage of person-years at risk on effective PrEP use, we define a similar parameter,

the percentage of person-years at risk exposed to detectable PrEP using the lower limit of quantitation (LLOQ) of the DBS assay.

Define the target parameter of interest as

$$\Phi(T) = \frac{\int_{T_0}^T p(t) E[Y(t)] dt}{\int_{T_0}^T E[Y(t)] dt}$$

where  $T_0$  is the time since the first person enrolled after DBS storage commenced,  $p(t)$  is the percent of participants on effective PrEP use at time  $t \in [T_0, T]$ , and  $E[Y(t)]$  is the expected number of participants with DBS storage at-risk for HIV at time  $t$ .

We estimate  $\Phi(T)$  based on the binary PrEP use readout from the DBS assay and the DBS sampling plan. Let  $i$ , ranging from 1 to  $N$ , index study participants and let  $j$ , ranging from 1 to  $M_i$ , index participant DBS collection dates that are sampled for assaying. For each sample collected, we have an indicator  $x_{ij}$  of effective PrEP use which is only measured if the DBS sampling indicator,  $\Delta_{ij}$ , is equal to 1. The estimated percentage of person-years at risk on effective PrEP use from the initiation of PrEP monitoring time  $T_0$  until time  $T$  is defined as

$$\hat{\Phi}(T) = \frac{\sum_{i=1}^N \sum_{j=1}^{M_i} \Delta_{ij} x_{ij} \pi_{ij}^{-1} P_{ij}}{\sum_{i=1}^N \sum_{j=1}^{M_i} P_{ij}}$$

where the sampling probability,  $\pi_{ij}$ , and person-years,  $P_{ij}$ , are defined below.

Let  $k$ , ranging from 1 to  $K$ , index the DBS sampling plan collection intervals  $[T_0, T_1]$ ,  $(T_1, T_2]$ ,  $\dots$ ,  $(T_{K-1}, T_K]$  where the right endpoint of each interval is a sample collection date (with  $T_K \equiv T$ ) and define  $\mathcal{T}_k$  as the  $k^{\text{th}}$  interval. Let  $t_{i1} < t_{i2} < \dots < t_{iM_i}$  be the sampling times in  $[T_0, T]$  for the  $i^{\text{th}}$  participant and define  $t_{i0}$  as the maximum of  $T_0$  and the  $i^{\text{th}}$  participants enrollment time. The DBS sampling plan determines which samples, collectively across participants, will be assayed for PrEP use. Define the set of samples,  $S_{ij}$ , as all samples collected during the same collection interval  $\mathcal{T}_k$  as the sample  $i, j$ . That is,  $S_{ij} \equiv \{i', j' | t_{i'j'} \in \mathcal{T}_k \text{ for } k \text{ s.t. } t_{ij} \in \mathcal{T}_k\}$ . Define the sampling probability as

$$\pi_{ij} \equiv \frac{\sum_{i', j' \in S_{ij}} \Delta_{i'j'}}{|S_{ij}|}$$

where  $|S_{ij}|$  is the number of samples in set  $S_{ij}$ . Define person-years,  $P_{ij}$ , as  $t_{ij} - t_{i(j-1)}$ . Note that our parameter of interest can be defined and estimated for the entire study cohort as well as for subregions (e.g., South African sites). We will report bootstrap 95% confidence intervals for  $\Phi(T)$ .

The same approach is used for point and confidence interval estimation of the percentage of person-years at risk exposed to detectable PrEP use.

An example of PrEP use report statistics are shown in Table 7.

Table 7: Summary of detectable and effective PrEP use

Number of DBS specimens collected over the 1 st batch period	$N_1$
Number of DBS specimens assayed over the 1 st batch period	$N_2$
Proportion of assayed specimens with TFV-DP above LLOQ (95% CI)	$N_3/N_2$ (x.xx, x.xx)
Proportion of assayed specimens with TFV-DP above effective use threshold* (95% CI)	$N_4/N_2$ (x.xx, x.xx)
Percent person-years on detectable PrEP through date T=xx (95% CI) #	$\widehat{\Phi}(T)_d$ (x.xx, x.xx)
Percent person-years on effective PrEP through date T=xx (95% CI) #	$\widehat{\Phi}(T)_e$ (x.xx, x.xx)
Repeat through N th batch period	

\*1000 fmol/punch

# $\widehat{\Phi}(T)_d$  is an estimate of the target parameter of interest based on measured TFV-DP above the LLOQ. Similarly,  $\widehat{\Phi}(T)_e$  is based on TFV-DP above the 1000 fmol/punch threshold for effective PrEP use.

